# 11.2.4. Secondary Effectiveness Endpoint 3: Symptomatic Recurrence

The third secondary effectiveness endpoint will evaluate the 12-month effectiveness rate when considering only documented symptomatic arrhythmia recurrences or interventions for arrhythmias as endpoint failures.

For this analysis endpoint events will be defined as:

- Acute procedural failure
- Use of non-study ablation catheter in the index procedure or in a repeat procedure during the blanking period
- More than one repeat procedure during the blanking period (90 days post index procedure)
- Documented symptomatic atrial fibrillation, or new onset of symptomatic atrial flutter or symptomatic atrial tachycardia between 91 days and 365 days post index procedure captured by one of the following methods:
  - ≥ 30 seconds in duration from the study specific event monitor or Holter Monitor
  - ≥ 10 seconds 12-lead Electrocardiography (ECG)
- Any of the following interventions for atrial fibrillation, or new onset of atrial flutter or atrial tachycardia between 91 days and 365 days post index procedure:
  - Repeat procedure
  - Electrical and/or pharmacological cardioversion
  - Prescribed any AAD\*
- \*AADs for endpoint will consist of all Class I/III, including Amiodarone, and any Class II/IV medications taken for control of atrial fibrillation (AF)/Atrial tachycardia (AT)/Atrial flutter (AFL) recurrence.

\*AADs for endpoint will consist of all Class I/III, including Amiodarone, and any Class II/IV medications taken for control of atrial fibrillation (AF)/Atrial tachycardia (AT)/Atrial flutter (AFL) recurrence.

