# 6.5. Primary Effectiveness Endpoint at 12 Months

The primary effectiveness endpoint at 12 months is defined as the event-free rate at 12 months (365 days) post-procedure.

Primary effectiveness events at 12 months are defined as:

- Acute procedural failure
  - Failure to achieve acute procedural success in the index procedure or in a repeat procedure during the blanking period.
  - Acute procedural success is defined as the achievement of electrical isolation of all PVs using the StablePoint catheter only. Electrical isolation of a PV is demonstrated by entrance block after 20 minutes waiting period. If exit block testing is performed, the PV will only be considered as isolated if both entrance and exit block testing are successful.
- Use of amiodarone post index procedure
- Use of non-study ablation catheter in the index procedure or in a repeat procedure during the blanking period.
- More than one repeat procedure during the blanking period (90 days post index procedure)
- Surgical ablation of Atrial Fibrillation (AF)/Atrial Tachycardia (AT)/Atrial Flutter (AFL) post index procedure
- Documented atrial fibrillation, or new onset of atrial flutter or atrial tachycardia between 91 days and 365 days post index procedure captured by one of the following methods:
  - ≥ 30 seconds in duration from the study specific event monitor or Holter Monitor

- ≥ 10 second 12-lead Electrocardiography (ECG)
- Any of the following interventions for atrial fibrillation, or new onset of atrial flutter or atrial tachycardia between 91 days and 365 days post index procedure:
  - Repeat procedure
  - Electrical and/or pharmacological cardioversion
  - Prescribed any AAD\*

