# 6.7. Secondary Endpoints

Secondary Endpoints include the following:

- Secondary Safety Endpoint SAE and AE Rates
- Secondary Effectiveness Endpoint 1 New or Increased Dose of AAD
- Secondary Effectiveness Endpoint 2 Single Procedure Success defined as freedom from primary effectiveness failure without a repeat procedure
- Secondary Effectiveness Endpoint 3 Symptomatic Recurrence: freedom from documented symptomatic AF/AT/AFL recurrence

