#### 11.2.2. Secondary Effectiveness Endpoint 1: New or Increased Dose of AAD

The first secondary effectiveness endpoint will evaluate the 12-month effectiveness rate when considering only newly prescribed or increased dosages of previously prescribed AADs as endpoint failures.

For this analysis endpoint events will be defined as:

- Acute procedural failure
- Use of non-study ablation catheter in the index procedure or in a repeat procedure during the blanking period
- More than one repeat procedure during the blanking period (90 days post index procedure)
- Documented atrial fibrillation, or new onset of atrial flutter or atrial tachycardia between 91 days and 365 days post index procedure captured by one of the following methods:
  - ≥ 30 seconds in duration from the study specific event monitor or Holter Monitor
  - ≥ 10 seconds 12-lead Electrocardiography (ECG)
- Any of the following interventions for atrial fibrillation, or new onset of atrial flutter or atrial tachycardia between 91 days and 365 days post index procedure:
  - Repeat procedure
  - Electrical and/or pharmacological cardioversion
  - Prescribed a new AAD\*
  - Prescribed an increased dose of a previously failed AAD\*

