# 11.2.3. Secondary Effectiveness Endpoint 2: Single Procedure Success

The second secondary effectiveness endpoint will evaluate the 12-month effectiveness rate when considering only subjects who do not require a repeat procedure within the blanking period as a success.

For this analysis endpoint events will be defined as:

- Acute procedural failure
- A repeat procedure during the blanking period (90 days post index procedure)
- Documented atrial fibrillation, or new onset of atrial flutter or atrial tachycardia between 91 days and 183\* days post index procedure captured by one of the following methods:
  - ≥ 30 seconds in duration from the study specific event monitor or Holter Monitor
  - ≥ 10 seconds 12-lead Electrocardiography (ECG)

\*AADs for endpoint will consist of all Class I/III, including Amiodarone, and any Class II/IV medications taken for control of atrial fibrillation (AF)/Atrial tachycardia (AT)/Atrial flutter (AFL)

- Any of the following interventions for atrial fibrillation, or new onset of atrial flutter or atrial tachycardia between 91 days and 365 days post index procedure:
  - Repeat procedure
  - Electrical and/or pharmacological cardioversion
  - Prescribed any AAD\*

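### The event list for single-procedure success (11.2.3) omits two primary failure items, so it does not deliver its section 6.7 definition; the same items are unaddressed in 11.2.2 and 11.2.4

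*Combined protocol and SAP*

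**What the plan says.** The 12-month primary failure list in 6.5 has two stand-alone items with no day window: "Use of amiodarone post index procedure" and "Surgical ablation of Atrial Fibrillation (AF)/Atrial Tachycardia (AT)/Atrial Flutter (AFL) post index procedure". The definitions table in 26.2 repeats both under Primary Effectiveness Failure, with the second worded as surgical treatment.

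The three secondary effectiveness endpoints are then specified as follows.

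- **Endpoint 2, single-procedure success.** Section 6.7, like the synopsis and Table 6-2, defines it as "Single Procedure Success defined as freedom from primary effectiveness failure without a repeat procedure". The list in 11.2.3 has four parts: acute procedural failure, any repeat procedure in the 90-day blanking period, documented recurrence, and interventions on days 91-365 (repeat procedure, cardioversion, any AAD). It has no separate item for amiodarone, surgical ablation or a non-study catheter.
- **Endpoint 1, AAD handling.** Section 11.2.2 gives the 12-month rate "when considering only newly prescribed or increased dosages of previously prescribed AADs as endpoint failures". Its AAD items are a new AAD or "Prescribed an increased dose of a previously failed AAD", on days 91-365.
- **Endpoint 3, symptomatic recurrence.** Section 11.2.4 describes itself as "considering only documented symptomatic arrhythmia recurrences or interventions for arrhythmias as endpoint failures". Its intervention item begins "Any of the following interventions for atrial fibrillation, or new onset of atrial flutter or atrial tachycardia between 91 days and 365 days post index".

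Sections 11.2.2 and 11.2.4 keep the non-study-catheter item and fail a subject for more than one blanking-period repeat. Neither has an amiodarone or surgical-ablation item. The AAD footnotes to the secondary lists name amiodarone among the Class I/III drugs. Section 11.2 calls all secondary analyses exploratory, with no powered hypotheses and no alpha adjustment.

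**The concern.** Under 6.7, single-procedure successes are a subset of primary successes, so the endpoint 2 rate cannot exceed the primary rate, and the gap between the two shows what the permitted second procedure contributed. Without the amiodarone and surgery items, 11.2.3 loses that subset property. The same subject can be classified in opposite ways depending on which section the programmer follows.

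For endpoints 1 and 3 the issue is narrower. Each states a purpose (AAD handling; symptoms). Neither purpose explains why surgical ablation is unlisted, and nothing says whether blanking-period amiodarone was left out on purpose. If these gaps are settled after the data are seen, the choice between definitions becomes post hoc.

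**Working it through.** No published figure is at issue, so the check compares the lists.

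**Step 1: items in the 6.5 list against each secondary list.**

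| 6.5 item | 11.2.2 | 11.2.3 | 11.2.4 |
|---|---|---|---|
| Acute procedural failure | yes | yes | yes |
| Amiodarone, any time after index | no | no | no |
| Non-study catheter | yes | no | yes |
| Blanking-period repeats | more than one | any | more than one |
| Surgical ablation, any time after index | no | no | no |
| Interventions, days 91-365 | yes, AAD narrowed | yes | yes |

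**Step 2: classify subjects.** Every subject below fails 6.5 and is assumed to have no other event. The documents do not say whether surgery is a repeat procedure, so both readings are shown.

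| Case | Endpoint 1 | Endpoint 2 | Endpoint 3 |
|---|---|---|---|
| Amiodarone confined to days 0-90 | not a failure | not a failure | not a failure |
| Amiodarone, days 91-365, for AF/AFL/AT | failure if new or increased | failure | failure |
| Amiodarone, days 91-365, other indication | not a failure | not a failure | not a failure |
| One surgical ablation, days 0-90; surgery is not a repeat | not a failure | not a failure | not a failure |
| One surgical ablation, days 0-90; surgery is a repeat | not failed by the repeat item (needs more than one) | failure | not failed by the repeat item (needs more than one) |
| Surgical ablation, days 91-365; surgery is not a repeat | not a failure | not a failure | not a failure |
| Surgical ablation, days 91-365; surgery is a repeat | failure | failure | failure |

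**Step 3: compare with the stated definitions.** Under 6.7, the whole endpoint 2 column should read failure. Two amiodarone rows do not on any reading, and two surgery rows do not on the narrow reading. In the endpoint 3 column, a single blanking-period surgery is an intervention for an arrhythmia, yet no intervention or repeat item counts it on either reading.

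**Step 4: the non-study-catheter item missing from 11.2.3.** Acute procedural success requires isolation with the study catheter only, so PV isolation completed with another catheter at index already fails. Use in a blanking-period repeat fails because any such repeat fails. What could remain is mainly non-PV use at index, and 26.2 limits the item to AF targets. This omission is largely redundant.

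**Step 5: size.** One subject among 299 moves a crude rate by 1/299 = 0.33 points. The documents give no frequency. If 1 to 6 subjects were affected (an assumption), the shift would be 1/299 = 0.3 to 6/299 = 2.0 points.

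**The case against.** **Amiodarone has not been dropped.** A reader might infer from the missing bullet that it no longer counts. That is wrong. Through the AAD footnotes, amiodarone for AF, AFL or AT on days 91-365 fails endpoints 2 and 3, and fails endpoint 1 if new or increased. Amiodarone within 60 days before enrollment is an exclusion, so later use will usually be new. Only use confined to blanking, or for another indication, escapes.

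**Endpoints 1 and 3 are meant to be narrower than the primary.** This stands. A primary failure who succeeds there because of an unchanged AAD dose or an asymptomatic recurrence is intended. No section says these lists are the primary list with a single substitution, and leaving blanking-period amiodarone out of endpoint 1 may be deliberate. What does not follow from their stated purposes is the silence on surgery.

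**Surgery may be covered elsewhere.** Section 10.7 treats an additional ablation procedure after blanking as an effectiveness failure, which favours the broad reading after day 90. If surgery were also a repeat procedure in blanking, the acute-procedural-failure item, which extends to such repeats and requires the study catheter only, might catch it by inference. But 6.5 lists surgery separately from repeat procedures, and no section states that reading.

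**The single-procedure rate will not necessarily exceed the primary rate.** A reader might infer that it will, but the documents do not show it. Through these items alone, otherwise event-free subjects who escape 11.2.3 would have to outnumber otherwise event-free subjects with one blanking-period repeat, who pass the primary and fail endpoint 2. Only the guarantee is lost. Separately, 11.2.3 counts documented recurrence only to day 183, against 365 in 6.5; that is a further mismatch in the same list.

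**The consequence is small.** This also stands. Amiodarone is prohibited after the procedure, so few subjects may be affected, and no secondary endpoint enters the success criteria in 6.6.

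**Conclusion.** The point holds firmly for endpoint 2: 11.2.3 and 6.7 classify some subjects in opposite ways, and 26.2 confirms that primary effectiveness failure includes both missing items. The clearest case is amiodarone confined to days 0-90, which needs no choice of reading. The surgery cases depend on whether a repeat procedure includes surgery, which is not stated.

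For endpoints 1 and 3 the finding is an unexplained gap, not a contradiction with the primary list as such. It is sharpest in endpoint 3, whose opening sentence says interventions for arrhythmias count.

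The size is about 0.33 points per affected subject on a crude rate with 299 subjects. Any total rests on assumed frequencies. Alpha, power, sample size, the primary endpoints and the study success criteria are all unaffected. This is a minor clarification, worth making because one endpoint has two incompatible definitions.

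**What to change.** - **Endpoint 2 (11.2.3):** define failure as the full 12-month list in 6.5, with any blanking-period repeat procedure counted in place of more than one. This restores agreement with 6.7 and 26.2, brings back the non-study-catheter item, and also removes the day-183 mismatch.
- **Endpoints 1 and 3 (11.2.2, 11.2.4):** add the surgical-ablation item from 6.5. Alternatively, state that a repeat procedure includes surgery and that not counting a single blanking-period surgery is intended.
- **Endpoints 1 and 3:** state whether amiodarone use in the blanking period is meant to be excluded from the failure events.

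The cost is wording only, in the protocol and the SAP. The data are already collected for the primary endpoint. Section 11.4.6 provides the route: an amended SAP approved before the analyses are performed.

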#### 11.3. General Statistical Methods

### 11.3.1. Analysis Sets

While each endpoint was individually powered, each safety endpoint analysis will use all available data from all ATTEMPT and TREATMENT subjects, and each effectiveness endpoint analysis will use all available data from all TREATMENT subjects.

## 11.3.2. Control of Systematic Error/Bias

#### 11.3.2.1. Control of Potential Bias

Selection of patients will be made from the Investigator's population. All patients meeting the eligibility criteria and having signed the ICF will be eligible for enrollment in the study. Control and reduction of potential bias associated with a single-arm study design have been taken into account by considering a series of measures including but not limited to:

- defining inclusion and exclusion criteria to represent a population similar to the one enrolled in recently completed trials on AF ablation;
- employing a rhythm surveillance monitoring strategy that is equivalent to that used in recent PAF IDE studies and consistent with the relevant recommendation in the HRS consensus document:
- utilizing core lab for reviewing electrocardiographic recordings from study specific rhythm surveillance monitoring after the blanking period.

#### 11.3.2.2. Control of Type I Error

Either of the primary effectiveness endpoints at 6 or 12 months must be met to achieve study success for PMA submission. Since each of these endpoints is tested at a one-sided significance level of 0.025, the family-wise type I error across both endpoints is maintained below 0.05. The primary safety endpoint at 30 days and the primary effectiveness endpoint for acute procedural success must also be met to achieve study success for PMA submission, and both endpoints will be tested at a one-sided significance level ≤0.05. Therefore, following the methodology of the Intersection-Union Test (IUT), the overall type I error across the study success for PMA submission criteria will be maintained below 0.05.

The criteria for overall study success are the same as that for study success for PMA submission, with the added conditions that the primary safety and effectiveness endpoints at 12 months must be met. Since both endpoints will be tested at a one-sided significance level of 0.025, the overall type I error across the overall study success criteria will be maintained below 0.05.

#### 11.3.3. Number of Subjects per Investigative Site

To avoid any center effect and bias, enrollment controls will be implemented to ensure no study site will be allowed to contribute more than 15% for the first 183 TREATMENT subjects (27 subjects/center) and then once 183 subjects are enrolled, no more than 15% of the remaining subject enrollment (44 subjects/center) of the total required enrollment.

# 11.4. Data Analyses

## 11.4.1. Six Month Analyses

A 6-month endpoint analysis is planned and will be conducted after all 299 TREATMENT subjects have completed 30 days of follow up and 183 TREATMENT subjects have completed their 6-month follow-up.

## 11.4.2. Subgroup Analyses

An analysis will be performed for the primary endpoints to determine whether significant differences exist in endpoint results between subgroups. The list of covariates (with applicable subgroups in parentheses) includes the following:

- Sex (Female vs. Male)
- Age at time of consent (subjects > 60 years vs subjects ≤60 years)
- Geography (International vs. United States)

Each subgroup covariate will be included as a single independent variable in a logistic regression model with the primary endpoint outcome as the dependent variable and a test for significance at the 15% level will be performed.

In addition to subgroup analyses, descriptive statistics of subject demographic and baseline characteristics will be presented for each subgroup listed in this section.

## 11.4.3. Justification of Pooling

Center-to-center heterogeneity will be assessed for the primary endpoints by performing a Chi-square test, treating site as a fixed effect. Descriptive statistics for each site will be presented but small sites (sites enrolling less than five subjects) will be excluded from the poolability analysis. If sites are not deemed poolable in the initial Chi-square analysis, the poolability analysis will be reperformed by treating site as a random effect. A significance level of 15% will be used for each test.

## 11.4.4. Multivariable Analyses

For each primary endpoint, univariate analyses of the following covariates will be performed, and any found to be significantly associated with the outcome at the 0.15 alpha level will be included as covariates in a multivariate regression model. Backward selection with 0.15 alpha level stay criterion will be used to determine the final multivariate model.

The list of baseline covariates includes, but is not necessarily limited to:

- Subject demographics (e.g. age, gender)
- Subject baseline characteristics (e.g. LVEF and LA diameter, cardiovascular disease histories and disease types)
- Procedural techniques (e.g., esophageal temperature monitoring)

## 11.4.5. Additional Analyses

Other additional endpoints and analysis include, but are not limited to:

- Changes in the quality of life measures (AFEQT and EQ-5D-5L) between baseline and 12 months follow up
- Total RF time for the index procedure (defined as the summation of all RF application durations)
- Total number of RF applications
- Total fluoroscopy time for the index procedure
- Total index procedure time
- Freedom from recurrence of individual types of atrial arrhythmias between 91 and 365 days from index procedure: 1) AF 2) AT 3) AFL
- Freedom from cardiovascular hospitalization at 12 months
- Quantification of parameters used during RF Application including RF power, RF duration, contact force and Local Impedance via DIRECTSENSE™ technology
- Descriptive summaries of primary safety and effectiveness endpoints at 12 months using the data available at the time of the 6-month analysis
- The predicted probability of success for the primary effectiveness endpoint at 12 months based off the data available at the time of the 6-month analysis.

Additional information on these analyses is included in the Statistical Analysis Plan.

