Single procedure success	Freedom from primary effectiveness failure without a repeat procedure.	To assess success rate after a single procedure.				
Symptomatic Recurrence	Freedom from documented symptomatic AF/AT/AFL recurrence	This is an analysis of a component of the primary effectiveness endpoint				
	Additional Endpoin	ts				
Quality of life assessment	Changes in the quality of life measures (AFEQT and EQ-5D-5L) between baseline and 12 months follow up	Consistent with the objective of AF ablation to improve quality of life and reduce AF-associated symptoms				
Individual arrhythmia recurrence rates	Freedom from recurrence of individual types of atrial arrhythmias between 91 and 365 days from index procedure: 1) AF 2) AT 3) AFL	This is an analysis of a component of the primary effectiveness endpoint				
Additional descriptive statistics	Total RF time, number of RF applications, total fluoroscopy time and index procedure time, quantification of parameters used during RF Application including RF power, RF duration, contact force and Local Impedance, Freedom from cardiovascular hospitalization at 12 months.	Analysis that are descriptive in nature and used to better characterize ablation procedure data, health data and the technology in use. The RHYTHMIA HDx TM Mapping System will be used to collect some of this information.				
Provide an estimate of the likelihood of success for the primary safety and effectiveness endpoints at 12 months at the time of the 6-month analysis.	Descriptive summaries of primary safety and effectiveness endpoints at 12 months using the data available at the time of the 6-month analysis  The predicted probability of success for the primary effectiveness endpoint at 12 months based off the data available at the time of the 6-month analysis.	Provides a measure of the completeness of follow-up, as well as an estimate of the likelihood of success for the primary safety and effectiveness endpoints at 12 months, at the time of the 6-month analysis.				

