## 11.1.4.2. Sample Size

The sample size estimate was obtained using the normal approximation to the binomial distribution and verified through simulations based on Kaplan-Meier methodology. The following assumptions were used in the sample size calculation:

Assumptions	Primary Safety at 12 Months
Expected rate	94%
Performance goal	89%
Attrition (per year)	10%
Significance level (one-sided)	2.5%
Power	80%
Sample size	299

Under the hypothesis and assumptions outlined above, the required sample size for this endpoint is 299 subjects treated with the IntellaNav StablePoint Catheter. This analysis drives the overall sample size for the NEwTON AF study.

The expected rate and performance goal for the primary safety endpoint at 12 months were determined using the meta-analysis outlined in Section 11.1.1 above and accounting for a 1% rate of safety events occurring between 30 days and 12 months.

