#### 11.1.4.3. Statistical Methods

The 12-month primary safety event-free rate will be calculated using Kaplan-Meier methodology. Subjects who withdraw from the study prior to 12 months without experiencing an event will be censored on the date of their last study visit. The 97.5% onesided lower confidence limit of the observed safety event-free rate at 12 months will be compared to the performance goal of 89%. If the lower confidence limit is greater than the performance goal, the null hypothesis will be rejected. The lower confidence limit will be calculated as the pointwise confidence limit using the log-log methodology.

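### Table 6-2 promises a likelihood of 12-month success for both safety and effectiveness at the 6-month analysis, but a predicted probability is planned for effectiveness only

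*Combined protocol and SAP*

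**What the plan says.** The last row of Table 6-2 (section 6.8) gives the objective as "Provide an estimate of the likelihood of success for the primary safety and effectiveness endpoints at 12 months", to be available at the 6-month analysis. The justification column of the same row says it again: "as well as an estimate of the likelihood of success for the primary safety and effectiveness endpoints at 12 months".

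The analyses meant to deliver this are listed in four places: the synopsis, the 6.8 list, the endpoint cell of the same Table 6-2 row, and 11.4.5. Each has two relevant items. One is "Descriptive summaries of primary safety and effectiveness endpoints at 12 months using the data available at the time of the 6-month analysis". The other is "The predicted probability of success for the primary effectiveness endpoint at 12 months based off the data available" at the 6-month analysis. Only the second is a likelihood of success, and in all four places it names effectiveness alone.

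On the endpoint left out, 11.1.4.2 plans 12-month safety at 80% power and one-sided 2.5%, with an expected event-free rate of 94%, a goal of 89% and 10% attrition per year, giving 299 subjects. It adds: "This analysis drives the overall sample size for the NEwTON AF study". The other four primary endpoints are planned at 90% power. Section 6.6.2 requires 12-month safety in both routes to overall success. The PMA submission criteria in 6.6.1 use 30-day safety only.

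**The concern.** A summary of 12-month safety at the snapshot reports the events seen so far. It does not give the probability that the final confidence limit will clear the goal. If the plan is followed as written, the safety half of the Table 6-2 objective is therefore not delivered.

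The omitted endpoint is the one for which an interim pass says least about its margin. The 30-day test uses a one-sided 95% limit against 90%. By 11.1.4.3, the 12-month test uses a one-sided 97.5% limit against 89%, and late events are added. A comfortable 30-day pass and a bare one mean very different things for month 12, and a predicted probability would put a number on that difference.

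**Working it through.** **Inputs.** 299 TREATMENT subjects, all with 30-day follow-up at the snapshot (11.4.1). 30-day safety: goal 90%, one-sided 5%, expected event rate 5% (11.1.1.2). 12-month safety: goal 89%, one-sided 2.5% (11.1.4.2, 11.1.4.3). Late events between 30 days and 12 months: 1% (11.1.4.2). Both limits are pointwise log-log.

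**The plan's own sample size.** One-sample normal approximation for 94% against 89%:

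n = [(1.960·√(0.89·0.11) + 0.842·√(0.94·0.06)) / 0.05]² = 264.5, so 265; 265/0.9 = 294.4, so 295.

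The plan states 299, within 2%. With 299 × 0.9 = 269 evaluable subjects the formula gives 80.8% power, and a Kaplan-Meier simulation at N=299 gives 82.4%. The stated 80% is sound.

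**Pass limits at N=299, no censoring.** With x events, S = 1 − x/299, se = √[x/(299(299 − x))], and the lower limit is exp{−exp[ln(−ln S) + z·se/|ln S|]}.

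- 30 days, z = 1.645: 21 events give 0.9010 (pass), 22 give 0.8971 (fail).
- 12 months, z = 1.960: 22 events give 0.8904 (pass), 23 give 0.8865 (fail).
- 12 months with the synopsis's 95% limit, z = 1.645: 23 events give 0.8933 (pass), 24 give 0.8895 (fail).

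A bare 30-day pass (21 events) thus leaves room for one late event (22 − 21), when about three are expected (0.01 × 299).

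**Chance of a 12-month pass after x events at 30 days.** P = Binomial CDF(c − x; 299 − x, 0.01), with c = 22 for the 97.5% limit and c = 23 for the 95% limit.

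| 30-day events | Late events allowed (97.5%) | P(12-month pass), 97.5% limit | P(12-month pass), 95% limit |
|---|---|---|---|
| 15 | 7 | 99% | >99% |
| 19 | 3 | 69% | 85% |
| 20 | 2 | 47% | 69% |
| 21 | 1 | 23% | 47% |

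**Averaged over 30-day passes.** Weighting by Binomial(299, 0.05) over x ≤ 21, P(12-month pass given 30-day pass) is 91.5% with the 97.5% limit and 95.4% with the 95% limit, so failure is 8.5% or 4.6%. The chance of exactly 20 or 21 events is 6.9%.

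**Sensitivity.** Applying the 1% to the 95% still event-free (0.01/0.95) gives 66%, 44% and 21% after 19, 20 and 21 events, and 90.7% on average. If the late rate were 2% (an assumption, again divided by 0.95), the chance would be 75% after 15 events, 29% after 18 and 2% after 21.

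**The case against.** The strongest reply is that nothing depends on the missing figure. It is an additional, non-confirmatory output. It appears in neither set of success criteria, and 6.6 places overall success after 12-month follow-up by design. This stands, and it sets the severity.

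A reader might infer that the safety risk would go unseen at submission. The documents do not support that: the planned descriptive summary would show the event count, and with the 11.1.4.3 rule one can see how near the limit it is. What is missing is the formal probability.

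A reader might also infer that safety is the endpoint about which least is known at the snapshot. That is not so. By the plan's rates, 5 of the 6 expected percentage points of safety events fall by day 30, when all 299 subjects are observed. For effectiveness it is 28 of 40 points by 6 months, with only 183 subjects required to have completed that visit. Safety is weaker only as the chance that an interim pass carries through to month 12 (90.7%, against 94.2% for effectiveness, on planned rates without censoring).

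The lowest-power statement rests on one-sided 2.5%, used in 11.1.4.2, 11.1.4.3 and 11.3.2.2. The synopsis applies a 95% limit to both safety time points. Under that limit simulated power is 91.9%, and 12-month safety would no longer be the least powered endpoint.

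Finally, the lists are open-ended, and 11.4.5 refers to a Statistical Analysis Plan for further detail. No separate plan is in the supplied text, so what it says on safety cannot be checked. Even so, every place that names the predicted probability limits it to effectiveness.

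**Conclusion.** The mismatch is exact and textual: the objective and its justification cover two endpoints, and the predicted probability covers one. Severity is low, and no conclusion of the trial is put at risk.

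The practical value of the missing figure is confined to narrow 30-day passes. At 20 or 21 events a 12-month failure is more likely than not under the 97.5% limit; under the 95% limit this holds only at 21. Such counts are uncommon at the planned rate, and most 30-day passes would lead to a 12-month pass.

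The figures assume 299 subjects with no censoring and no ATTEMPT subjects added to the safety set, a 1% late-event rate, and no use of the late follow-up already in the snapshot. They illustrate what the prediction would show; they are not a forecast. The textual point depends on none of them.

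**What to change.** In the synopsis, 6.8, the Table 6-2 endpoint cell and 11.4.5, extend the item to the predicted probability of success for the primary safety and the primary effectiveness endpoints at 12 months. Compute both from the same 6-month snapshot. State the prediction method, and for safety use the 97.5% one-sided limit of 11.1.4.3. Correct the synopsis, which applies a 95% limit to 12-month safety.

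If the sponsor does not want a safety prediction, narrow the Table 6-2 objective and justification to effectiveness. Either change should be made before the snapshot, since a prediction added or dropped afterwards would look data-driven.

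The cost is a phrase in four places, one extra computation from data already held, and possibly a less favourable safety figure on view at submission.
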